## Description of Subject Population

### Sample #1

Specify subject population

Older adults with hearing loss and depression

Number of completers required to accomplish study aims

32

Projected number of subjects who will be enrolled to obtain required number of completers

40

Age range of subject population

$\geq 60$

Gender, Racial and Ethnic Breakdown

On the basis of previous studies conducted in the Clinic for Aging, Anxiety, and Mood Disorders (CAAM) (formerly the Late Life Depression Research Clinic [LLDRC]) at the New York State Psychiatric Institute (NYSPI) and Columbia University, it is anticipated that the sample at this site will be composed of approximately 75% Caucasian, 15% African American, and 10% Hispanic subjects.

On the basis of previous studies conducted in the CAAM, it is anticipated that the sample recruited will be composed of 60% women and 40% men.

Description of subject population

This study will enroll 40 outpatients who (1) are aged  $\geq 60$  years, (2) diagnosed with Diagnostic and Statistical Manual (DSM) 5 MDD or Persistent Depressive Disorder, (3) have duration of depression  $\geq 6$  months, (4) have 24-item Hamilton Rating Scale for Depression (HRSD) score  $\geq 16$ , (5) have moderate to severe unilateral or bilateral hearing loss (combined PTA  $> 50$ dB at 2 and 3 kHz), (6) demonstrate impaired speech discrimination scores (60-100% on 25 word list testing) in one or both ears, (7) no history of hearing aid use within the past 6 months, (8) English speaking, and (9) are willing to and capable of providing informed consent and complying with study procedures. Exclusion criteria are (1) diagnosis of substance abuse or dependence (excluding Tobacco Use Disorder) within the past 12 months, (2) history of psychosis, psychotic disorder, mania, or bipolar disorder, (3) diagnosis of probable Alzheimer's Disease, Vascular Dementia, or Parkinson's Disease, (4) Mini Mental Status Examination (MMSE)  $\leq 24$  (66), (5) current or recent (within the past 4 weeks) treatment with antipsychotics or mood stabilizers, (6) current suicidal ideation (HRSD suicide item  $> 2$ ) with risk of imminent self-harm, (7) any physical or intellectual disability adversely affecting ability to complete assessments, (8) acute, severe, or unstable medical or neurological illness, (9) contraindication to hearing aid placement, and (10) significant retrocochlear pathology or

organic brain lesion (e.g., acoustic neuroma) responsible for hearing loss.

## Recruitment Procedures

Describe settings where recruitment will occur

The studies described will be conducted conjointly at (1) the Otolaryngology and Neurotology Clinical Practice at the Columbia University Medical Center (CUMC) and (2) the Clinic for Aging, Anxiety, and Mood Disorders (CAAM) at the New York State Psychiatric Institute (NYSPI).

How and by whom will subjects be approached and/or recruited?

Participants will be recruited in 3 possible ways: (1) patients presenting with hearing problems to the Columbia Otolaryngology and Neurotology Clinical practice who are found to have comorbid depressive symptoms, (2) patients presenting with depression to the Clinic for Aging, Anxiety, and Mood Disorders (CAAM) who are found to have comorbid hearing problems, and (3) patients that have been referred or are responding to study advertisement (through flyers, newspaper, RecruitMe advertising, Bus Shelter advertising, the MindMate online application, radio ads, and ResearchMatch.com) who endorse hearing problems and comorbid depressive symptoms.

Regarding (1), [name] or one of her staff will check the audiometric data that was already collected for clinical purposes for a patient whom she is seeing in the Columbia Otolaryngology and Neurotology Clinical Practice to check whether the patient potentially meets hearing eligibility criteria. If so and the patient also reports subjective feelings of loneliness, social isolation, or depression, a PHQ-9 can be conducted and [name] will verbally ask the patient whether he/she would be willing to speak with the research team regarding a study. If the patient says yes, then the research team will speak with the patient to schedule an evaluation in the CAAM. Re: (2), if a patient under evaluation in the CAAM appears otherwise eligible and interested, they will be scheduled for a hearing evaluation in the Columbia Otolaryngology Clinical Practice to confirm hearing eligibility. Re: (3), patients who have been referred or are responding to study advertisement will be scheduled for evaluation in the CAAM. If a patient has outside audiometric data from the past 12 months, it will be checked by [name] or one of her staff to determine whether the patient meets hearing eligibility criteria. If a patient does not have recent audiometric data, he/she will be scheduled for a hearing evaluation in the Columbia Otolaryngology Clinical Practice or will be asked to schedule a hearing evaluation with a doctor of their choice to confirm hearing eligibility.

Once an individual has been found eligible to participate, Dr.s [name], [name], [name], [name], or [name], NP, MPH will meet with the patient to discuss the risks, benefits, and alternatives to study participation and invite them to participate. Of note, the consent discussion process will include discussion of the technology HIPAA-compliant video conferencing to be used for remote visits and any concerns the participant may have, such as access to a private space in which to take calls, or accessibility—access at home to adequate devices, cell signal, or wifi. The consent discussion process will also include any COVID-19 risks related to travel and in-person visits for research purposes, as well as ensuring patients are aware that treatment is available outside of the protocol.

How will the study be advertised/publicized?

Flyers posted around CUMC, RecruitMe, advertisements in local newspapers, referrals from CUMC

clinicians, advertisement on Facebook, advertisement in Bus Shelters, the MindMate online application, radio ads, and ResearchMatch.com.

Do you have ads/recruitment material requiring review at this time?

Yes

Does this study involve a clinical trial?

Yes

Please provide the NCT Registration Number

NCT03321006

### Concurrent Research Studies

Will subjects in this study participate in or be recruited from other studies?

No

### Inclusion/Exclusion Criteria

Name the subject group/sub sample

Patients

Create or insert table to describe the inclusion criteria and methods to ascertain them

Characteristic	Method of Ascertainment
1. aged $\geq$ 60 years	1. clinical interview
2. diagnosed with Diagnostic and Statistical Manual (DSM) 5 MDD or Persistent Depressive Disorder	2. scid, clinical interview
3. have duration of depression $\geq$ 6 months	3. clinical interview
4. have 24-item Hamilton Rating Scale for Depression (HRSD) score $\geq$ 16	4. HRSD
5. have moderate to severe unilateral or bilateral hearing loss (combined PTA of $>$ 50dB at 2 and 3 kHz)	5. audiometric testing
6. demonstrate impaired speech discrimination scores (60-100% on 25 word list testing) in one or both ears	6. audiometric testing
7. no history of hearing aid use within the past 6 months	7. clinical interview
8. English speaking	8. clinical interview

9. are willing to and capable of providing informed consent and complying with study procedures 9. clinical interview

Create or insert table to describe the exclusion criteria and methods to ascertain them

Characteristic	Method of ascertainment
1. diagnosis of substance abuse or dependence (excluding Tobacco Use Disorder) within the past 12 months	1. scid, clinical interview
2. history of psychosis, psychotic disorder, mania, or bipolar disorder	2. scid, clinical interview
3. diagnosis of probable Alzheimer’s Disease, Vascular Dementia, or Parkinson’s Disease	3. clinical interview, MMSE
4. Mini Mental Status Examination (MMSE) ≤ 24	4. MMSE
5. current or recent (within the past 4 weeks) treatment with antipsychotics or mood stabilizers	5. clinical interview
6. current suicidal ideation (HRSD suicide item > 2) with risk of imminent self-harm	6. HRSD, clinical interview
7. any physical or intellectual disability adversely affecting ability to complete assessments	7. clinical interview
8. acute, severe, or unstable medical or neurological illness	8. clinical interview
9. contraindication to hearing aid placement	9. clinical interview
10. significant retrocochlear pathology or organic brain lesion (e.g., acoustic neuroma) responsible for hearing loss	10. clinical interview
11. having contraindication (e.g. metal) or unable to tolerate the scanning procedures	11. MRI safety screening form

**Waiver of Consent/Authorization**

Indicate if you are requesting any of the following consent waivers  
Waiver of consent for use of records that include protected health information (a HIPAA waiver of Authorization)

No

Waiver or alteration of consent

No

Waiver of documentation of consent

No  
Waiver of parental consent  
No

**Consent Procedures**

Is eligibility screening for this study conducted under a different IRB protocol?

Yes

Indicate NYSPI IRB #

6395R

Describe Study Consent Procedures

[name], [name], [name], [name], or [name], NP, MPH will explain the study procedures along with the attendant risks, benefits, and alternatives, including the anticipated outcome of doing nothing. The consenting physician will then leave the room while the potential subject reads the consent form and return to answer any questions the subject has. Subjects who wish to participate will sign the consent form, while those who do not wish to participate will simply not participate.

**COVID-19 Phase 1 Re-Opening:**

If an individual is deemed eligible for Protocol #7540 after completing the IRB approved virtual portion of the general evaluation (Protocol #7284R), they will be consented into the study. We are requesting to make an adjustment to the consent procedures to accommodate REDCap e-consenting for participants who have a computer and email access. Participants who cannot complete e-consent due to lack of appropriate technology access will be consented on the day of the in-person portion of the evaluation. The consenting clinician will explain the study procedures along with the attendant risks, benefits, and alternatives, including the anticipated outcome of doing nothing. They will also ensure that patients are aware that treatment is available outside the protocol. The consent process will include discussion of the HIPAA-compliant video conferencing to be used for remote visits and any concerns the participant may have, such as access to a private space in which to take calls, or accessibility—access at home to adequate devices, cell signal, or wifi. The consent discussion process will also include any COVID-19 risks related to travel and in-person visits for research purposes.

Indicate which of the following are employed as a part of screening or main study consent procedures

✓ Consent Form

## Study Procedures

Describe the procedures required for this study

### Overview

Following baseline evaluation and MRI scanning, each subject will be counseled on the role of antidepressant medications in clinically significant depressive disorders as well as the risks and benefits of starting/changing antidepressant medication. Subjects will be randomized to receive antidepressant medication (AD) in combination with either full amplification hearing aids or low amplification hearing aids. Subjects who do not wish to change their antidepressant medication will also be offered participation in a subgroup of the study and will be randomized to receive either full amplification hearing aids or low amplification hearing aids. Subjects, treating clinicians, and depressive/cognitive outcome assessors will be blinded to hearing aid assignment. At randomization (Week 0) subjects will have devices placed and receive education by an audiologist, who will not be blinded but will conduct identical procedures for full vs. low amplification hearing aids and will maintain the blinding with participants. Subjects will have follow up audiology appointments at Weeks 2, 6, and 12 to receive further education, monitor compliance, and ensure devices are working correctly. Failure to adhere to hearing aid use requirements at Weeks 2 and/or 6 (as determined by the usage data log), or any hearing aid complications will prompt an additional audiology appointment at Week 9. At Weeks 2, 4, 6, 9, and 12 subjects will complete depression follow-up visits. However, a weekly CGI severity score of 6 or 7 will prompt a weekly session to check-in with the subject.

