#### Hearing aid procedures

1. For audiological assessment, the patient will be seated in a double walled soundproof booth. Pure tone testing will be performed using insert earphones and bone conducted stimuli. Frequencies tested include 250 Hz, 500 Hz, 1k Hz, 2k Hz, 3k Hz, 4k Hz, 6k Hz and 8 k Hz. Speech reception thresholds (SRT) will be

obtained in each ear using standard spondee words. Word recognition will be assessed in each ear using a recorded CNC (consonant-vowel nucleus-consonant) type word list (25 words) at 40dB SL above the patient's SRT. Screening: subjects will have testing of pure tone thresholds, SRT, and word recognition as above.

2. At Week 0, The Hearing Handicap Inventory for the Elderly (HHIE) (77) will be administered, which is a 10-item questionnaire developed to assess how an individual perceives the social and emotional effects of hearing loss. Unaided word recognition will be tested using CNC at 50dB HL and AzBio sentences (condition 1: signal 50dB HL in quiet, condition 2: signal 50dB HL with a +5 SNR using 4 talker babble), both presented at 0° azimuth.

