4. Subjects will have follow up audiology appointments at Weeks 2, 6, and 12, during which their questions about hearing aid usage will be answered and the data log will be checked and reset. At Week 6, if the hearing aid devices are functioning well and the patient is meeting the usage requirement, the audiologist will ask if the patient would like to skip the Week 9 audiology visit and return at Week 12. However, if the patient's hearing aid use does not meet the requirement at Weeks 2 and/or 6 (as determined by the data log) or if there are any hearing aid complications, they will be scheduled for an audiology visit at Week 9. At Week 12, endpoint measures will be collected, which comprise the HHIE and repeat of audiological measurements from Week 0.

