#### MRI procedures

1. Participants will undergo an MRI scan at baseline and study endpoint (prior to unblinding).

2. Image Acquisition: MRI of the brain will be conducted using the following sequences: (1) Axial IR-FSPGR TE/TR=3ms/6.5ms, TI=450ms, flip angle=12°, voxel size=1x1x1mm, 180 contiguous slices, total acquisition time=4min; (2) Multi-Band (or Simultaneous Multi-Slice) EPI, TE/TR=30/800ms, flip angle=52°, matrix=90x90, voxel size=2.4x2.4x2.4mm, acquisition time=5min(rs-fMRI)/7min(task-fMRI); (3) for DWI, TE/TR=88ms/4100ms, voxel size=1.7x1.7x1.7mm, flip angle=90°, FOV=240x240 mm, matrix=140x140, diffusion directions=102, b value=1000s/m^2, acquisition time=7.5min, (4) 3D T2-weighted FLAIR, TE/TR=144/8000ms, voxel size=1x1x1mm, acquisition time=8 min. During the fMRI scanning, subjects' wakefulness will be monitored using a MR-compatible eye-tracking camera.

3. Simon Task: For the Simon Task, a series of white arrows pointing either left or right is displayed against a black background either to the left or right of a white gaze fixation cross-hair positioned at midline. Stimuli are 'congruent' (arrows pointing in the same direction as their position on the screen) and 'incongruent' (pointing in a direction opposite their position on the screen). Each experiment contains 3 runs, totaling 66 incongruent and 66 congruent stimuli. Participants are instructed to respond as quickly as possible to the direction of the arrow by pressing one of 2 buttons on a response box. Stimulus duration is 1300ms, with jittered inter-stimulus intervals ranging from 4 to 7 seconds. Behavioral outcome measures are reaction times (RT) and accuracy scores on congruent and incongruent trials, and the Simon effect (mean RT incongruent > mean RT congruent).

4. Subject Comfort: For the MRI procedures, the subject will be instructed to lie as still as possible within the magnet for approximately 30 minutes. When we position a subject in the scanner, head movement will be minimized through: (a) instructions to the participant; and (b) packing the head inside the head coil with

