### End of study procedures

1. At the end of the 12 week study, participants will be notified the group to which they were assigned (low amplification or full amplification). Participants in the low amplification group will meet with the study audiologist to have their hearing aids set to full gain as per standard clinical practice. All participants will be allowed to keep their hearing aids and will have clinical follow up visits scheduled in the Columbia Otology clinic as per routine practice. Patients will use their insurance or otherwise cover the costs of their clinical audiologic care as they normally would outside the context of a research study. However, the study will cover one post-protocol audiology visit for participants in the low-amplification group in order to ensure the devices are working correctly and to answer questions the patient may have about their newly working devices.
2. Patients will also receive the typical 3 months post-protocol open treatment in the CAAM. Depending on their clinical status, options to continue, augment, switch, or begin the study antidepressant medication will be discussed with patients.

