#### Week 12:

This visit will be completed in two components, one in-person and one virtual. During the in-person portion, the participant will complete the endpoint neuropsychological (NIH Toolbox DCCST and Flanker, RBANS-H) and physical (SPPB, Gait Speed) measures, which must be completed in-person with a research staff member. The remainder of the Week 12 visit will be conducted virtually with both a research staff member and study clinician. If necessary, the Week 12 virtual visit may become an in-person visit, at the discretion of the clinician. The audiology appointment will remain an in-person visit.

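### HHIE sits in the unblinded audiologist's visits with no collector named; self-completion at the psychiatric visits and a stated order at Weeks 0 and 12 would reduce expectation bias, though not remove it

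*Protocol*

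**What the plan says.** **Who is blinded.** The protocol's Overview states: "Subjects, treating clinicians, and depressive/cognitive outcome assessors will be blinded to hearing aid assignment". It says that at Week 0 participants "receive education by an audiologist, who will not be blinded but will conduct identical procedures for full vs. low amplification hearing aids"; the same sentence makes the audiologist responsible for keeping participants blind. Assessors of hearing outcomes are not mentioned.

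**Where HHIE is collected.** It appears under Hearing aid procedures. Item 2 reads "At Week 0, The Hearing Handicap Inventory for the Elderly (HHIE) (77) will be administered" and describes a 10-item questionnaire on the person's own perception of the social and emotional effects of hearing loss. Item 4, which covers the audiology appointments, says of Week 12 that "endpoint measures will be collected, which comprise the HHIE" together with the repeat audiological tests. HHIE is not in the list of measures for the psychiatric follow-up visits (Study Assessments, item 3).

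**How it is analysed.** The SAP's Data Analysis section uses HHIE as its worked example: an ANCOVA of change from Week 0 to Week 12 on baseline, group, age and education.

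**What must precede unblinding.** MRI procedures, item 1: "Participants will undergo an MRI scan at baseline and study endpoint (prior to unblinding". No other measure carries this wording. End of study procedures, item 1, has participants told their group when the 12 weeks are over, and adds: "Participants in the low amplification group will meet with the study audiologist to have their hearing aids set to full gain". The COVID-19 Week 12 section says "This visit will be completed in two components, one in-person and one virtual", with audiology as a further in-person appointment. It gives no sequence.

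**The concern.** HHIE asks how handicapped a person feels, so the answers can be coloured by what the participant expects and by the setting in which the form is given. Its setting is a visit with someone who programmed the device, knows the arm and has counselled the participant. The protocol protects depressive and cognitive ratings by blinding their assessors but gives HHIE no such protection, although the SAP tests it between arms in the same way.

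The second, smaller issue is order. The audiologist who sees the participant at Week 12 also resets low-amplification devices. If notification or reset came before the remaining Week 12 measures, those measures would be taken without the blind. A reset before the partly oral cognitive battery (RBANS-H) would also change test conditions in one arm only. The protocol does not plan this, but apart from the MRI rule nothing in it states the order.

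**Working it through.** This is mainly a question of reading sections together. The arithmetic is only an illustration.

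**Step 1: collector of HHIE.** The blinded roles are participants, treating clinicians and depressive/cognitive assessors. HHIE is not a depressive or cognitive measure, and both mentions of its collection are in the passive voice. The placement points to the audiology visit, but the documents do not say who hands out or scores the form.

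**Step 2: whether a blinded alternative exists.** Psychiatric visits take place at Weeks 0 and 12 (Study Assessments, item 2). Under the COVID-19 provisions a research staff member and a study clinician attend the virtual part of both. Participants already complete self-report scales (IDS-SR and the Social Adjustment Scale) at psychiatric visits, so a 10-item form can follow the same route.

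**Step 3: order at Week 12.** Four things need an order: the audiology endpoint tests, the in-person neuropsychological and physical tests, the virtual psychiatric ratings, and the notification with device reset. The text places notification at the end of the 12 weeks and requires only the MRI to come before unblinding.

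**Step 4: order at Week 0.** Devices are placed at Week 0. HHIE is now listed beside unaided word recognition, which suggests that it comes before fitting. If it moved to the psychiatric visit without an ordering rule, the baseline form could be completed after fitting, which would contaminate both the baseline covariate and the change score.

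**Step 5: illustration of size.**

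Inputs from the protocol (Description of Subject Population): 40 enrolled to obtain 32 completers. The implied loss is 8/40 = 20%, and 32/(1 − 0.20) = 40. The 20% is back-calculated, not stated. Equal arms give n = 16 completers or 20 enrolled per arm.

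Inputs assumed, because the documents give none: two-sided alpha 0.05, no true HHIE effect, and a between-arm shift b in units of the residual SD.

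Model: two-arm ANCOVA with the SAP's three covariates (baseline, age, education).
- Degrees of freedom: 2n − 2 − 3, so 27 at n = 16 and 35 at n = 20.
- Noncentrality: b/√(2/n). At n = 16, b = 0.2 gives 0.2/0.354 = 0.57 and b = 0.3 gives 0.85.
- False-positive rate: the probability that a noncentral t exceeds the two-sided 5% critical value in either direction.

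| Assumed shift b | n = 16 | n = 20 |
|---|---|---|
| 0 | 5.0% | 5.0% |
| 0.1 | 5.9% | 6.1% |
| 0.2 | 8.5% | 9.4% |
| 0.3 | 13.0% | 15.2% |
| 0.5 | 27.6% | 33.7% |

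If the collection setting caused half of the shift and the change removed only that half, the rates at n = 16 would be 5.9% (total shift 0.2), 6.9% (0.3) and 10.5% (0.5). They return to 5.0% only if collection setting and visit order cause all of it.

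**The case against.** The case on the other side is substantial. A reader might infer that the audiologist collects HHIE. The documents do not say so, and they do not exclude self-completion. The person who rates HHIE is the participant, who is blinded, and the audiologist must follow identical procedures in both arms and keep participants blind. HHIE is in no aim or hypothesis, and the SAP does not call it primary.

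A reader might also infer that the plan allows the depression and cognitive outcomes to be rated after disclosure. The text does not support that either. Notification is placed at the end of the 12 weeks, the blinding statement makes no exception for Week 12, and clinician and participant guesses of the arm are collected at the psychiatric visits, which makes sense only while the blind holds. Nor does the Week 12 section say that its components fall on different days. What is missing is an ordering sentence.

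These points lower the weight of the concern but do not close it. A blinded participant can still be influenced by an unblinded person present when the form is completed, and a general duty to keep the blind is weaker than keeping that person out of data collection.

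**Conclusion.** The point holds as a modest weakness with a cheap remedy. HHIE is subjective, is compared between arms, and is placed in visits run by an unblinded audiologist, with no collector named and no blinded role covering hearing outcomes. The missing Week 12 order is mostly absent detail, best settled in the same edit.

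Two stronger conclusions are tempting. The first is that moving the form removes the bias. It does not: unblinded fitting, education and counselling continue at Weeks 0, 2 and 6 and sometimes 9. Participants may also guess their arm, since the low-amplification setting is described as giving a small audible increase without real gain in speech discrimination. The second is that HRSD and CGI are compromised. The collector issue does not touch them, since their assessors are blinded; only the unstated Week 12 order could, and nothing shows that it would.

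The size of the bias cannot be determined from the documents. The rates in the table follow from assumed shifts and say nothing about how likely such a shift is.

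**What to change.** 1. In Hearing aid procedures, state that participants complete HHIE themselves at the Week 0 and Week 12 psychiatric visits, with research staff who are blinded to assignment, and not at the audiology appointment. Use the same method at both time points.
2. State that the Week 0 form is completed before the devices are fitted.
3. Extend the MRI rule on unblinding to every Week 12 measure: HRSD, CGI, IDS-SR, Social Adjustment Scale, neuropsychological and physical tests, HHIE, audiological tests, and the final clinician and participant guess of the arm. All are to be recorded before group notification and device reset.
4. Report the HHIE comparison beside the blind-guess data, since some expectation bias will remain.

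The cost is wording and a fixed order of appointments at Weeks 0 and 12, which makes scheduling less flexible. No new visit is needed. Extra staff look unnecessary because people already attend both visits, but the documents give no workload figures to confirm this. The word recognition and sentence tests would stay with the audiologist.
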